For reduction in skin sensitivity (allodynia), pain thresholds will be determined 2 hours after DFN-15 or placebo treatment. Since the detection of pain thresholds depends on subjective data input, several algorithms have been developed in order to minimize subjective variation, and make the results as objective as possible. These algorithms are incorporated into the software program that controls the thermal and mechanical sensory analyzer (Q-Sense 2016). Changes in skin sensitivity will be determined by comparing corresponding pain thresholds obtained in the pain-free session (baseline) to pain thresholds obtained during migraine, first before (untreated migraine) and then after (treated migraine) treatment with DFN-15 or placebo. In healthy subjects, pain thresholds for heat and mechanical skin stimuli range between 42-47 °C (107.3-116 °F) ([Lindblom, 1994](#)), and 75-281 g ([Strigo et al., 2000](#)), respectively. Using a more stringent criteria, we will consider a patient to be allodynic if her/his pain threshold is below 41 °C (105.8 °F) for heat, and below 30 g for skin indentation with the calibrated von Frey hairs. Meeting the criterion for any one of modality will be sufficient to determine that the patient is allodynic at the 'during untreated migraine' testing. For this endpoint, the database will consist of pain threshold measurements in 50 patients, taken while they are pain-free (baseline), during untreated migraine attack (before DFN-15 or placebo treatment), after treatment with DFN-15 or placebo. Only those patients who completed all 3 testing sessions will be included in the data analysis. The resulting distributions will be tested for normality, and their descriptive statistics computed. The differences

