between before and after DFN-15 treatment will be computed on a pair-wise basis. To increase the sensitivity of detecting changes, patients in this study will be compared to themselves (baseline vs. during untreated migraine vs. during treated migraine) rather than to control subjects because the large normative range of pain thresholds reduces the sensitivity of detecting allodynia in reference to the normal range. Differences between pain-free vs. during untreated migraine vs. during treated migraine will be computed on a multiple sample pair-wise basis. Differences in mean pain threshold will be judged (significant or not significant) by using appropriate pair-wise multiple sample comparison (Newman-Keuls, Kruskal-Wallis) tests. Alternatively, repeated measurements of pain thresholds (allodynia) will be analyzed using Friedman two-way analysis of variance. Finally, secondary analyses using the collected data may be done as a part of this study including, but not limited to, the duration and intensity of the headache prior to arrival at the clinic.

The primary outcome measure in the current study is the proportion of patients demonstrating a headache intensity decrease that is greater than 50% (post-treatment compared to pre-treatment). Secondary outcome measures are proportions of patients demonstrating allodynia before and after treatment; allodynia to thermal stimuli is defined as a pain threshold < 41 0C, and to mechanical stimuli as pressure pain threshold of < 30 g.

The primary and secondary outcome measures will be examined using the Z test for comparison of independent proportions and Chi-square (χ^2) test to assess the categorical association between the group (treatment / placebo) and (i) reduction rate of headache intensity (below / above 50%; primary outcome measure); (ii) proportion of thermally allodynic participants (pain threshold below / above 41 0C; secondary outcome measure); and (iii) proportion of mechanically allodynic participants (pressure pain threshold below / above 30 g; secondary outcome measure).

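### Kruskal-Wallis, an independent-groups test, is named for pain thresholds taken three times in the same patients, so the plan gives up the pairing it relies on for sensitivity

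*Combined protocol and SAP*

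**What the plan says.** All of this is in the Data analysis section of the combined protocol and SAP.

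- **Design of the comparison.** For skin sensitivity, "patients in this study will be compared to themselves (baseline vs. during untreated migraine vs. during treated migraine) rather than to control subjects". The reason given is "because the large normative range of pain thresholds reduces the sensitivity of detecting allodynia in reference to the normal range".
- **Data.** "Only those patients who completed all 3 testing sessions will be included in the data analysis", so every analysed patient contributes a full set of three measurements.
- **Tests named.** Differences in mean threshold are to be declared significant or not by "appropriate pair-wise multiple sample comparison (Newman-Keuls, Kruskal-Wallis) tests". The next sentence adds: "Alternatively, repeated measurements of pain thresholds (allodynia) will be analyzed using Friedman two-way analysis of variance". Nothing says which of these decides, and no pairwise test is attached to Friedman here.
- **Contrast with headache intensity.** The same section gives that repeated measure Friedman followed by the Wilcoxon matched-pairs signed-ranks test.
- **Status.** The opening paragraph of the section makes reduction in skin sensitivity one of two primary endpoints. A later paragraph makes the headache responder proportion the primary outcome and allodynia proportions secondary.

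**The concern.** Kruskal-Wallis takes its reference distribution from independent samples. Here the three samples are the same people. The between-patient spread, which the plan wants to remove by self-comparison, goes back into the yardstick against which the change is measured. If a patient's three readings are positively correlated, the test becomes conservative and loses power.

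At stake is the second objective, whether late treatment reverses allodynia. It turns on three contrasts: untreated against pain-free, treated against untreated, and treated against pain-free. The only pairwise procedures named for them are Kruskal-Wallis and Newman-Keuls, and the plan does not say that Newman-Keuls would use a repeated-measures error term. A modest treatment change, or a treated threshold still somewhat below the pain-free level, could be called not significant because of the test used.

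**Working it through.** **1. The plan's own figure.** The only computed figure is the sample size, 9 placebo and 36 treated, for headache response of 30% against 80% (one-tailed 5%, 90% power, 4:1).

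- Pooled proportion: (9 × 0.3 + 36 × 0.8)/45 = 0.70.
- SE under no difference: √[0.70 × 0.30 × (1/9 + 1/36)] = 0.1708.
- SE under the alternative: √[0.3 × 0.7/9 + 0.8 × 0.2/36] = 0.1667.
- z = (0.50 − 1.645 × 0.1708)/0.1667 = 1.31, which is power of 90.6%.

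The figure reproduces. It concerns independent arms and does not depend on the threshold tests. No power figure is given for those.

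**2. Inputs for the threshold tests.**

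- From the plan: three sessions per patient, complete cases only, and enrolment ending at 40 DFN-15 and 10 placebo completers.
- Assumed, because the plan gives none: normal thresholds, a common within-patient correlation ρ of 0.3, 0.5 or 0.7, shifts in SD units, two-sided 5% tests, and analysis within each arm.

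**3. Why Kruskal-Wallis is mis-sized, in closed form.** With equal correlation and no true difference, its statistic behaves approximately as (1 − ρs) × χ² on 2 df, where ρs = (6/π) arcsin(ρ/2) is the rank correlation. For 2 df, P(χ² > c) = exp(−c/2), so the rejection rate is 0.05^[1/(1 − ρs)].

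- ρ = 0.3: ρs = 0.288, rate 1.5%.
- ρ = 0.5: ρs = 0.483, rate 0.3%.
- ρ = 0.7: ρs = 0.683, rate 0.01%.

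**4. Simulation.** Thousands of trials per setting, with simulation error of one to two points. The dip is in the untreated session only.

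| Setting | Test | ρ = 0.3 | ρ = 0.5 | ρ = 0.7 |
|---|---|---|---|---|
| n = 40, no difference | Kruskal-Wallis | 1.5% | 0.5% | 0.0% |
| n = 40, no difference | Friedman | about 5% | about 5% | about 5% |
| n = 40, 0.5 SD dip | Kruskal-Wallis | 59% | 58% | 57% |
| n = 40, 0.5 SD dip | Friedman | 63% | 79% | 94% |
| n = 10, 0.5 SD dip | Kruskal-Wallis | 11% | 8% | 5–6% |
| n = 10, 0.5 SD dip | Friedman | 16–18% | 23% | 35% |

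The simulated false-positive rates agree with step 3.

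**5. A single pair 0.5 SD apart, n = 40** (for example treated still below pain-free, unadjusted). The unpaired rank test detects it about 59% to 65% of the time across these correlations. The signed-rank test detects it 72%, 85% and 97% of the time.

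**6. Residual allodynia after a large dip, n = 40.** Shifts are 0, −1.5 and −0.5 SD, and the contrast is treated against pain-free, Bonferroni-adjusted for three pairs. Kruskal-Wallis with Dunn comparisons detects it 26%, 21% and 18% of the time. Friedman with signed-rank detects it 56%, 71% and 93%.

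**7. Where the loss disappears.**

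- At ρ = 0 nothing is lost: with shifts 0, −0.5 and −0.25 SD and n = 40, Kruskal-Wallis has 49% power against 37% for Friedman.
- With a 1 SD dip and n = 40, both omnibus tests detect it in about 100% of trials for ρ from 0.3 to 0.7.
- With a 1 SD dip and n = 10 at ρ = 0.5, a gap remains: 51% against 71%.

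**The case against.** The strongest reply is that a valid test, Friedman, is already in the plan. The allodynia cut-offs (41 °C and 30 g, against healthy ranges of 42–47 °C and 75–281 g) also suggest shifts large enough for any test to find. Both points carry weight. If Friedman is the test relied on, the omnibus problem goes away, and a 1 SD dip in 40 patients is safe either way. Neither point settles the matter. No rule makes Friedman decisive, no paired test follows it for thresholds, and a large dip does not protect the treated against pain-free contrast, as step 6 shows.

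A reader might infer more than the documents support:

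- **That the test almost never rejects.** This is true only when there is no difference. At a 0.5 SD dip and n = 40 it still detects a little under 60%.
- **That the choice of tests inflates false positives.** Taking the better of the two rank tests named stays near 5% at n = 40 for these correlations. A rate of 6.5% to 6.8% appears only if repeated-measures ANOVA is added, which the plan does not name.
- **That a normality check selects the test.** The plan says "The resulting distributions will be tested for normality, and their descriptive statistics computed" and attaches no choice of test to it. The fair criticism is that there is no selection rule at all.
- **That a non-significant result will be declared reversal.** Nothing in the plan equates the two; allodynia is defined by fixed cut-offs.
- **That the proportion tests should be paired.** The plan says "Secondary outcome measures are proportions of patients demonstrating allodynia before and after treatment", but the Z and chi-square tests it specifies relate outcome to treatment group. Those are independent groups, so a McNemar test would add an analysis without correcting one.
- **That Newman-Keuls is wrong in itself.** It is usable on a repeated-measures error term; the plan omits to say so.

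**Conclusion.** Wrong as written; should be fixed. The named test does not match the data structure the plan itself describes, and the unranked alternative does not repair that.

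The direction is firm for any positive within-patient correlation, which the self-comparison presupposes: the false-positive rate falls below 5%. The size is not firm, because correlation, SD and effect are all assumed. For a 0.5 SD dip in 40 patients, the omnibus loss against Friedman runs from 4 points at ρ = 0.3 (63 − 59) to 37 points at ρ = 0.7 (94 − 57). The practical harm is confined to small changes, residual allodynia and the 10-patient placebo arm.

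The point ranks below a must-fix. The error is conservative for any claim of change, a valid test is already listed, and neither the headache responder outcome nor the between-arm comparisons are touched. It still matters because the plan in one place calls skin sensitivity a primary endpoint.

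**What to change.** In the threshold paragraph of Data analysis:

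1. Delete Kruskal-Wallis for the within-patient comparison.
2. Pre-specify one paired analysis for each modality (heat, mechanical). One option, in line with the headache-intensity analysis, is Friedman over the three sessions, then Wilcoxon signed-rank on untreated against pain-free, treated against untreated, and treated against pain-free, with Holm adjustment.
3. Report each pair as a paired difference with a 95% confidence interval, so that a residual deficit is read from its size as well as its p-value.
4. Keep Newman-Keuls only if the text states that it uses a repeated-measures error term. A repeated-measures ANOVA or mixed model would also be acceptable if named in advance. On normal data with a 0.5 SD dip and n = 40, repeated-measures ANOVA detects 91% to 98.5% for ρ of 0.5 to 0.7, so Friedman is not the only sound choice.
5. Remove the open alternative, or state the rule that picks between methods, before unblinding.

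The cost is a wording change. No extra patients, visits or measurements are needed, and the sample size stands.

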Screening visit - In the first appointment we will identify patients who are good candidate to participate in the study and measure their pain thresholds following an initial evaluation. This appointment will allow us to train patients in how the quantitative sensory testing is performed.

‘During-migraine’ visit – In the second appointment patients’ headache intensity, associated symptoms, and mechanical and heat pain thresholds will be tested 180 min after the onset of a migraine headache. Pain threshold will be determined within the referred pain area in the head. These tests will provide the pre-treatment data to be compared later with post-treatment data. Once pain thresholds are established, patients will be treated and their headache intensity, associated symptoms and pain thresholds will be re-examined 120 minutes later.

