Throughout the treatment and testing the patients will be monitored (vitals, etc.) to ensure their safety. If a member of the control group is in excruciating pain and their migraine is intolerable they will be prescribed a rescue medication. In this case the participant will drop out of the study. The participants will have the option to drop out at any point in the study. At the end of the testing (5 hours after migraine onset), if a participant (from either group) is still symptomatic and in pain, they will have the opportunity to have a rescue medication prescribed by one of the specialists at the Headache Center. In the case that a patient does not respond well to the study treatment they will be monitored for at least 1 hour before leaving the clinic.

Data analysis:

Primary endpoint: There are 2 primary endpoints in this study. The first is reduction in headache intensity after DFN-15 treatment, and the second is reduction in skin sensitivity at 2 hours after DFN-15 treatment.

For reduction in headache intensity, level of pain will be documented at 1 and 2 hours after treatment using a visual analogue scale of 0 (no pain) to 10 (worst pain). Comparisons of these ordinal (repeated) measures will be performed using Friedman two-way analysis of variance followed by Wilcoxon matched-pairs signed-ranks test.

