Power analysis was based on the Z test for comparison of independent proportions. Incorporated were α of 5% (significance level), 1- β error probability of 90% (power), and allocation ratio of 4:1 (treatment:placebo, respectively). Based on previously published data ([name] et al., Annals of Neurology 2004), the primary outcome measure is expected to be lower in the treatment group; accordingly, power analysis was one-tailed. The primary hypothesis was that post-intervention proportions of patients demonstrating a headache intensity decrease that is greater than 50% in the treatment and placebo groups would be 80% and 30%, respectively. This computation yielded a required number of 9 subjects in the placebo group and 36 patients in the treatment group (critical Z = -1.645). An additional 20% were accounted for potential dropout. Thus, a total of 54 participants (11 placebo, 43 treatment) are to be enrolled in the entire study.

References:

[name] R, Collins B, Jakubowski M. 2004. Defeating migraine pain with triptans: a race against the development of cutaneous allodynia. *Ann Neurol* 55(1):19-26.

[name] R, Yamamura H, Malick A, Strassman AM. 1998. Chemical stimulation of the intracranial dura induces enhanced responses to facial stimulation in brain stem trigeminal neurons. *Journal of Neurophysiology* 79(2):964-982.

[name] R, Yarnitsky D, Goor-Aryeh I, Ransil BJ, Bajwa ZH. 2000. An association between migraine and cutaneous allodynia. *Annals Neurol* 47:614-624.

Schroeder BM. 2003. AAFP/ACP-ASIM release guidelines on the management and prevention of migraines. *American family physician* 67(6):1392, 1395-1397.

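### The graded headache score is called a primary endpoint but is tested only within patients, so the plan never compares it between DFN-15 and placebo

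*Combined protocol and SAP*

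**What the plan says.** All references are to the combined protocol and SAP.

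- **Scores collected.** At the during-migraine visit (Study design), "headache intensity, associated symptoms, and mechanical and heat pain thresholds will be tested 180 min after the onset of a migraine headache". This is the pre-dose score. Under Data analysis, Primary endpoint, "level of pain will be documented at 1 and 2 hours after treatment using a visual analogue scale" running from 0 to 10.
- **Status of the score.** The same paragraph lists two primary endpoints; the first is reduction in headache intensity.
- **Analysis of the score.** "Comparisons of these ordinal (repeated) measures will be performed using Friedman two-way analysis of variance followed by Wilcoxon matched-pairs signed-ranks test". No other analysis of the 0-10 values is given.
- **Comparison between arms.** Later in Data analysis: "The primary outcome measure in the current study is the proportion of patients demonstrating a headache intensity decrease that is greater than 50"%. Its link with arm is assessed as "reduction rate of headache intensity (below / above 50%; primary outcome measure"), and "The primary and secondary outcome measures will be examined using the Z test for comparison of independent proportions and Chi-square". No covariate is named.
- **Power.** The power paragraph is built on the responder proportion: "Incorporated were α of 5% (significance level), 1- β error probability of 90% (power), and allocation ratio of 4:1", one-tailed, with 80% and 30% responders, giving 36 and 9 patients.

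**The concern.** Friedman's test ranks each patient's own scores across time points, and the Wilcoxon matched-pairs test looks at each patient's own change. Neither has a term for arm. A clear fall from pre-dose to 2 hours would be credited to DFN-15, although attacks ease by themselves and the plan itself expects 30% of placebo patients to improve by more than half.

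Running the tests separately in each arm does not help. With 40 patients on drug and 10 on placebo, a significant result in one arm and not in the other can arise from the numbers alone.

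The stake is that a trial carried out exactly as written would report a primary endpoint with no randomised evidence behind it. The one randomised headache result would rest on about 0.30 x 10 = 3 placebo responders and would carry no estimate in points.

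**Working it through.** **Which contrast each test makes**

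| Quantity | Named test | Contrast |
|---|---|---|
| 0-10 scores | Friedman, Wilcoxon matched pairs | time points within patient |
| Decrease above 50%, yes/no | Z, chi-square | DFN-15 vs placebo |
| 0-10 scores | none | DFN-15 vs placebo |

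**Inputs from the documents.** Responders 80% vs 30%; alpha 5%, one-tailed; power 90%; ratio 4:1 (power paragraph). The study stops at 40 DFN-15 and 10 placebo completers (Randomized controlled trial paragraph). No score SD, pre-post correlation or score distribution is given.

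**1. The plan's own figure.** Pooled proportion = (0.30 + 4 x 0.80)/5 = 0.70.
Placebo n = [1.645 x sqrt(0.21 x 1.25) + 1.282 x sqrt(0.21 + 0.16/4)]^2 / 0.50^2 = (0.843 + 0.641)^2 / 0.25 = 8.8, so 9 placebo and 36 treated. The stated size reproduces.

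**2. Responder test at 40:10.** Null SE = sqrt(0.21 x (1/40 + 1/10)) = 0.162. Alternative SE = sqrt(0.16/40 + 0.21/10) = 0.158.
- One-sided: (0.50 - 1.645 x 0.162)/0.158 = 1.48, power 93.0% (92.7% by exact enumeration).
- Two-sided: (0.50 - 1.960 x 0.162)/0.158 = 1.15, power 87.6% (86.6% exact).

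**3. Within-arm tests at 40:10.** For the same mean change and spread, a paired statistic on DFN-15 is sqrt(40/10) = 2 times that on placebo. This holds exactly for a paired mean and approximately for Wilcoxon. Identical behaviour in both arms can therefore look like a drug effect.

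**4. Between-arm ANCOVA at 40:10.** Simulation, 8,000 trials per scenario (Monte Carlo SE about 0.4 points), all calibrated to 80% and 30% responders. Assumed: pre-dose score about normal, mean 6.5, SD 1.5, limited to 3-10; the post-treatment score is the 2-hour score, limited to 0-10.

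| Assumed shape of 2-hour/pre-dose ratio | Responder Z, two-sided | ANCOVA, two-sided |
|---|---|---|
| Normal shift, SD 0.2 | 86.7% | 95.8% |
| Normal shift, SD 0.3 | 86.5% | 95.6% |
| Normal shift, SD 0.4 | 86.2% | 95.4% |
| Two groups, ratios 0-0.5 and 0.5-1.2 | 86.1% | 74.0% |
| Two groups, ratios 0-0.3 and 0.6-1.0 | 86.0% | 81.1% |
| Two groups, ratios 0-0.2 and 0.8-1.0 | 87.0% | 85.0% |

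Further two-group runs with whole-number scores gave ANCOVA 76-83% against 83-87% for the Z test. One-sided, the normal-shift cases give about 98% (ANCOVA) against 92-93% (Z).

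**5. What the ANCOVA estimate would deliver.** The 95% CI half-width is about 2.01 x SD x sqrt(1/40 + 1/10) = 0.71 x SD, with t on 47 df. Taking the residual SD as about 6.5 x 0.2 = 1.3 to 6.5 x 0.4 = 2.6 points gives 0.9 to 1.8 points, before the floor at 0 narrows it. The covariate also handles chance imbalance: with an assumed pre-dose SD of 1.5 to 2, the arm difference in mean pre-dose score has SE 0.35 x SD = 0.53 to 0.71 points.

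**The case against.** The strongest reply is that nothing is wrong with the responder test. A fall of more than half is a legitimate and readable outcome, the trial was sized on it, the sizing reproduces, and on the plan's one-tailed basis it has about 93% power at 40:10, above the 90% target. All of this stands.

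A reader might infer that cutting the score at 50% throws away power, taking it from about 95% to about 87%, and that ANCOVA should therefore replace the responder test. The documents do not support that. The 95% needs a roughly normal, equal-spread shift, the kind of model that favours the graded score. With the same responder rates and a two-group pattern, ANCOVA does no better and usually worse. That pattern is not far-fetched: Objective 1 asks whether the drug terminates attacks, and the Background speaks of making patients pain-free.

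Nor should one infer that the plan ignores the pre-dose score. It is the reference for the percent decrease; only a covariate is missing. Even in the favourable model most of the gain comes from keeping the score graded, and the covariate adds roughly 1 to 4 points of power.

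Two cautions also stand. Linear ANCOVA on a bounded score with 10 placebo patients had a simulated false-positive rate of 4.4-6.4%, hence the permutation p-value. And a further confirmatory test would add multiplicity, hence the supportive label.

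The plan does argue for comparing patients with themselves, but it makes that argument for pain thresholds, not headache. None of these points supplies the missing arm comparison of the graded score.

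**Conclusion.** The concern holds as a gap in the analysis, not as a fault in the responder test or the sample size. A primary endpoint of a randomised trial is assigned tests that cannot compare the arms. This follows from the text alone and rests on no assumption.

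The effect on power is conditional: better by about 9 points two-sided (about 5 one-sided) under a normal shift, and lower by about 2 to 12 points in the two-group scenarios tabulated. The choice between these rests on a score distribution that the documents do not give, so neither a power gain nor an underpowered design should be claimed. What is certain is a randomised, baseline-adjusted difference in points with a confidence interval, which the plan does not now produce.

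**What to change.** In the Primary endpoint paragraph of Data analysis:

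1. Replace Friedman and Wilcoxon as the named analysis of the graded score with a between-arm ANCOVA of the 2-hour 0-10 score on arm and pre-dose score.
2. Report the adjusted difference in points with its 95% CI, and a p-value from permuting arm labels.
3. State that the proportion with a decrease above 50% is the single confirmatory primary test and that the ANCOVA is supportive, so no multiplicity is added.
4. If the within-patient tests are kept, call them descriptive.

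Settle this before unblinding. The cost is SAP wording and one model on scores already being collected, with no extra patients, visits or measurements. The downside is one more reported result, which may differ in strength from the responder result; naming the confirmatory analysis in advance prevents a choice between them afterwards.

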Individuals with episodic migraine will be considered for participation in this study. Primary inclusion criteria will be (1) age 18-64 years old, (2) history of migraine with or without aura, based on the International Classification of Headache Disorders (3rd edition) for at least 3 years, (3) two or more migraine attacks per month on average during the previous year, and (4) ability to communicate in English (in order to understand and follow instructions of testing). Exclusion criteria will include: (1) fifteen or more headache days per month; (2) aspirin or NSAID-induced asthma or allergy; (3) pregnancy and/or lactating; (4) history of coronary artery bypass surgery, heart attack, angina, stroke, serious gastrointestinal bleeding, peptic ulcer disease; or chronic kidney disease; (5) having medical conditions requiring use of diuretics or daily anticoagulants; (6) having severe uncontrolled medical problems or medications that may influence measurements or impair ability to participate in the testing (e.g. daily or frequent use of opiates or barbiturates (>8 days per month), or NSAIDs or other analgesics (>14 days per month); known creatinine > 2.5 mg/dl or GFR < 30, severe peripheral neuropathy, dementia, etc.); and (7) having been advised by a health professional not to use COX-2 inhibitors.

Potential participants will be recruited from the Hartford Healthcare Headache Program.

Randomized controlled trial: After screening, which will be performed on a non-migraine day, participants will be randomized in a double-blinded fashion to receive either the active drug (DFN-15) or placebo in a ratio of 4:1. They will be instructed to return to the

clinic during a migraine. At the ‘during-migraine’ visit, which will begin 3 hours after onset of headache, we will document headache intensity, associated symptoms, and mechanical and heat pain threshold (first) before treatment (at 180 min after onset of headache) and (second) at a 120 min after treatment (5 hours after headache onset). Based on our prior experience studying migraine patients, we plan to screen 100 patients to achieve 50 participants completing the 2 study visits as planned. 80/100 patients will be randomized to receive the active drug and 20/100 patients will receive the placebo. The study will be terminated as soon as the first 40 patients who received the DFN-15 and first 10 patients who received placebo completed visit 2.

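### The planned enrolment of 54 (43/11) and the rule to stop at 40 and 10 completers cannot realistically both be followed

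*Combined protocol and SAP*

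**What the plan says.** The Randomized controlled trial paragraph (under Participant selection) gives one set of numbers:

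- Screening plan, where the 50 are those who finish both visits: "Based on our prior experience studying migraine patients, we plan to screen 100 patients to achieve 50 participants".
- Allocation: "80/100 patients will be randomized to receive the active drug and 20/100 patients will receive the placebo".
- Stopping rule, under which the trial is "terminated as soon as the first 40 patients who received the DFN-15 and first 10 patients who received placebo completed visit 2".

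The Data analysis section follows the same target for the skin-sensitivity endpoint: "the database will consist of pain threshold measurements in 50 patients". It limits the analysis to completers: "Only those patients who completed all 3 testing sessions will be included in the data analysis".

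The power paragraph at the end of Data analysis gives another set:

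- Required number: "This computation yielded a required number of 9 subjects in the placebo group and 36 patients in the treatment group".
- Allowance for loss: "An additional 20% were accounted for potential dropout".
- Resulting enrolment figure: "Thus, a total of 54 participants (11 placebo, 43 treatment) are to be enrolled in the entire study".

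**The concern.** The document carries two completer targets (50 and 45) and two headline numbers (100 and 54). It also has two different allowances for patients who do not complete, and nothing links them. The power paragraph presents 54 as the figure for the whole study. The stopping rule is set by completers in each arm and has no upper limit on enrolment.

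Site staff would have to follow one and breach the other. If they follow the stopping rule, they will almost surely randomise more than 54. Any approval or drug-supply figure taken from the power paragraph would then be too low. If they stop at 54, the 40/10 rule and the 50-patient database will very probably be missed. In a trial with about ten placebo patients, the end of recruitment should not be open to choice.

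**Working it through.** **1. Reproducing the required number.** Inputs from the power paragraph: one-tailed 5% (critical Z 1.645 in size), 90% power (1.282), 4:1 allocation, response 80% against 30%. The pooled proportion is (0.3 + 4 × 0.8)/5 = 0.70.

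Placebo n = [1.645 × √(0.70 × 0.30 × 1.25) + 1.282 × √(0.3 × 0.7 + 0.8 × 0.2/4)]² / 0.5² = (0.843 + 0.641)² / 0.25 = 8.80, rounded up to 9. DFN-15 n = 4 × 9 = 36. The plan's 36/9 reproduces.

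**2. Reproducing 54.** 36 × 1.2 = 43.2, rounded to 43; 9 × 1.2 = 10.8, rounded to 11; 45 × 1.2 = 54. This also reproduces. It leaves 45 if 9 of 54 are lost (16.7%). If 20% of the 54 are lost, 54 × 0.8 = 43.2 remain. Dividing by 0.8 would give 45/0.8 = 56.25, so 57.

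**3. The two sets side by side.**

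| | Randomized controlled trial paragraph | Power paragraph |
|---|---|---|
| Starting number | 100 screened, allocated 80/20 | 54 enrolled, 43/11 |
| Completers | 50 (40/10) | 45 (36/9) |
| Implied loss | 50%, screened to completed | 16.7% (20% added on) |

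**4. Can 43/11 give 40/10?** At most 3 of 43 and 1 of 11 may be lost. Assume independent losses at the same rate in both arms, with completion probability c. The chance is P[Bin(43, c) ≥ 40] × P[Bin(11, c) ≥ 10].

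| Loss | DFN-15 arm | Placebo arm | Both | At least 50 of 54 in total |
|---|---|---|---|---|
| 20% | 0.018 | 0.322 | 0.6% | 1.0% |
| 16.7% | 0.057 | 0.431 | 2.4% | 4.1% |
| 10% | 0.365 | 0.697 | 25% | 36% |
| 7.4% (54 to 50) | 0.604 | 0.806 | 49% | 63% |

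The joint chance reaches 50% at a loss of about 7.3%. It falls below 5% once loss exceeds about 14.9%.

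**5. Power.** Exact power of the pooled one-tailed Z test at 80% against 30% is 90.3% at 36/9 and 92.7% at 40/10. Averaged over binomial losses from 43/11, it is 90.4% at 16.7% loss and 89.3% at 20%.

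**6. How many must be randomised to reach 40/10?** The plan does not give the randomisation method, so two were simulated: 4:1 in blocks of 5, and simple 4:1. The number at which mean completers per arm meet the target is 40/0.8 = 50 and 10/0.8 = 12.5, rounded up to 13, total 63, at 20% loss. At 50% loss it is 40/0.5 = 80 and 10/0.5 = 20, total 100.

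| Loss after randomisation | Mean completers meet 40/10 at | Blocks of 5: median (95th percentile) | Simple: median (95th percentile) |
|---|---|---|---|
| 20% | 63 | 65 (77) | 68 (95) |
| 50% | 100 | about 106 (139) | about 110 (154) |

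Under blocking, 63 is enough in about 42% of trials at 20% loss, and 100 in about 32% at 50% loss. More than 54 are needed in about 98% of trials at 16.7% loss and over 99% at 20%.

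**The case against.** The best defence is that 100 counts patients screened and 54 counts those enrolled. The plan does speak of screening 100. With a screening visit meant to find suitable candidates and a list of exclusions, some screen failures must be expected. On that view the 80/20 split of 100 is a loose restatement of 4:1. If 54 are enrolled and 50 complete, the loss is only 4/54 = 7.4%, and 40/10 is then close to an even chance.

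Part of this stands. The step from 100 to 50 is a yield from screening to completion, not a stated completion rate among those randomised. It is therefore wrong to say that 54 fails at every rate one could draw from the document. But the defence does not reconcile the sections. The plan literally allocates all 100, and the power paragraph's own allowance takes 54 to 45, not 50. The 7.4% arises only from forcing the two figures together.

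It is also fair that 36/9 already meets the stated 90% power. The 50-patient database is described for the skin-sensitivity endpoint, not the powered responder outcome. The document itself gives no supply or ethics figures, so harm to those is conditional.

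A reader might infer that the trial is underpowered, since 54 enrolled with half completing would average about 74% power. The documents do not support that: no section combines 54 enrolled with 50% completion. Nor do they show that 100 patients must be randomised, because the experience cited covers screening to completion only.

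**Conclusion.** The contradiction is real and unreconciled, but it is an enrolment and stopping problem, not a power problem. At the loss the power paragraph allows for, 54 enrolled has a 0.6% to 2.4% chance of delivering the 40/10 completers that end the study. Only a loss of about 7% or less gives an even chance or better, and the plan states no such rate. The required 36/9 is arithmetically sound.

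The probabilities assume independent loss at one rate in both arms. The power figures assume the plan's one-tailed test at 80% against 30%. The numbers needed to reach 40/10 also depend on an assumed randomisation method. The matter should be settled before recruitment relies on either figure.

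**What to change.** 1. Keep the 40/10 completer rule as the governing target. Aligning the rule to 36/9 would also be coherent, at about 90% power. If the sponsor prefers that, the 50-patient database must change with it.
2. Delete the 54 (43/11) from the power paragraph.
3. State in both places one number to be randomised, by arm, with one assumption for loss after randomisation. Define screened, randomised and completed separately, and present the 100-to-50 ratio as a screening yield if that is what is meant. In that case reword the 80/20 allocation of all 100.
4. If the 20% loss is kept, give 63 (50/13), described as the number at which mean completers meet the target. Add the likely range: median about 65 and 95th percentile 77 with blocks of 5, or 68 and 95 with simple randomisation. If the sponsor believes half of those randomised will complete, give 100 (80/20), with about 106 and 139, or about 110 and 154. Neither number should be called a cap or the expected number needed.
5. State the randomisation method, so that one range applies.
6. State that 36/9 is the minimum for 90% power and that 40/10 gives about 93%.

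The cost is a short amendment and a larger stated enrolment, with any supply or approval figures set to cover the upper range. The 4:1 allocation, the point of randomisation and the stopping rule stay as they are.
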